9.1 Discontinuation

9.1.1 Discontinuation of study treatment

Discontinuation of study treatment for a patient occurs when study treatment is stopped earlier than the protocol planned duration. Discontinuation of study treatment can be decided by either the patient or the Investigator. If discontinuation of study treatment occurs, the investigator must determine the primary reason for the patient's premature discontinuation of study treatment and record this information on the Dosage Administration CRF.

Patients who discontinue study treatment or who decide they do not wish to participate in the study further should NOT be considered withdrawn from the study UNLESS they withdraw their consent. Where possible, they should return for the assessments indicated by an asterisk (*) in the assessment table (safety follow up and end of study visits). If they fail to return for these assessments for unknown reasons, every effort (e.g. telephone, e-mail, letter) should be made to contact the patient/pre-designated contact as specified. This contact should preferably be done according to the study visit schedule.

Cohort A

Study treatment must be discontinued under the following circumstances:

- Patient decision Patients may choose to discontinue study treatment for any reason at any time.
- The Investigator believes that continuation would negatively impact the safety of the patient or the risk/benefit ratio of trial participation.
- Any protocol deviation that results in a significant risk to the patient's safety.
- Pregnancy
- Infections that are considered, by the investigator, not efficiently manageable while being on LNP023
- Worsening of C3G disease
- Use of prohibited treatment as outlined in Table listing prohibited medications
- Any laboratory abnormalities that in the judgment of the investigator, taking into consideration the patient's overall status, prevents the patient from continuing participation in the study

Cohort B

Study treatment must be discontinued under the same circumstances as Cohort A plus the below:

• Histologic signs of graft rejection \geq 2A BANFF and other signs of graft rejection that require increased doses of concomitant immunosuppressive therapies.

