12.1 Analysis sets

For all analysis sets, subjects will be analyzed according to the study treatment(s) received for Cohort A and B.

The safety analysis set will include all subjects that received any study drug.

The PK analysis set will include all subjects with available PK data and no protocol deviations with relevant impact on PK data.

The PD analysis set will include all subjects with available PD data and no protocol deviations with relevant impact on PD data.

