12.4.3 Handling of missing values/censoring/discontinuations

The primary analysis will include all available data up to the point of treatment discontinuation for patients who discontinue.

Commercially Confidential Information

Subjects with missing UPRC or C3 Deposit Score values will still be included in the mixed model analysis with such data assumed missing at random (MAR).

Commercially Confidential Information

Given the severe nature of the indication and the need for close monitoring it is expected that there will be very little truly missing data.

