## 4 Statistical methods: Analysis sets

For all analysis sets, subjects will be analyzed according to the study treatment(s) received for Cohort A and B.

The safety analysis set will include all subjects that received any study drug.

The PK analysis set will include all subjects with available PK data and no protocol deviations with relevant impact on PK data.

The PD analysis set 1 will include all subjects with available PD data and no protocol deviations with relevant impact on PD data, as well as no serious adverse event

The PD analysis set 2 will include all subjects with available PD data and no protocol deviations with relevant impact on PD data.

Table 4-1	Protocol deviation codes and analysis sets	
Category Deviation c	Text description of deviation ode	Data exclusion
Subjects are	excluded from PK analysis in case of these PDs:	Exclude subject from PK analysis set
Subjects are	excluded from PD analysis in case of these PDs:	Exclude subject from PD 1 and PD2 analysis sets
COMD02	Prohibited concomitant medication-4	Yes
Subjects are PDs:	excluded from PK and PD analysis in case of these	Exclude subject from PK and PD analysis sets

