## 6 Statistical methods for Pharmacodynamic (PD) parameters

All subjects within the PD analysis set 1 will be included in the PD data analyses of primary and secondary objectives.

All subjects within the PD analysis set 2 will be included in the PD data analyses of exploratory objectives.

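### For prohibited medication, SAP Table 4-1 deletes the whole subject from both PD sets; this fits protocol 12.1 but conflicts with 12.4.3 and can discard valid Day-28 UPCR data in Cohort A

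*SAP*

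**What the plan says.** SAP section 4, Table 4-1, shows one code in the block for PD exclusions: COMD02, "Prohibited concomitant medication-4". The action is "Exclude subject from PD 1 and PD2 analysis sets". The unit is the subject, and the visible text sets no limit by when the drug was taken. SAP section 6 then states: "All subjects within the PD analysis set 1 will be included in the PD data analyses of primary and secondary objectives". PD set 2 serves the exploratory objectives, so a subject with this code enters no PD analysis that uses either set.

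Three protocol sections bear on the same patient:

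- 9.1.1 lists, among the circumstances in which study treatment must stop, "Use of prohibited treatment as outlined in Table listing prohibited medications".
- 12.4.3 says: "The primary analysis will include all available data up to the point of treatment discontinuation for patients who discontinue". It also keeps subjects with missing values in the mixed model under a missing-at-random assumption.
- 12.1 says: "The PD analysis set will include all subjects with available PD data and no protocol deviations with relevant impact on PD data".

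The Cohort A model (SAP 6.1.3) has two post-baseline time points, Day 28/29 and Day 84/85. The Cohort B primary test uses the change in C3 Deposit Score at the Week-12 biopsy.

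**The concern.** Taken together, protocol 9.1.1 and 12.4.3 tell the analyst to keep what was collected before a patient stopped for prohibited treatment. Table 4-1 tells the analyst to delete all of it. For a Cohort A patient with a Day-28 collection on treatment, the two instructions give different data sets for the primary analysis.

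The choice matters because Table 4-1 makes membership of the analysis set depend on something that happens after baseline, in an open-label single-arm cohort with no control arm to expose the effect. If prohibited drugs are started more often in patients who are responding poorly, deletion leaves a better-looking group, and the estimated UPCR ratio moves in favour of LNP023.

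**Working it through.** **1. Which patients the two rules treat differently**

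The schedule in protocol Table 8-1 has 24-h urine collections at baseline (Day -1 to Day 1), Day 28 and Week 12, apart from an optional screening one.

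| First use of the prohibited drug, patient then stops | 12.4.3 keeps | Table 4-1 keeps | Difference in the primary analysis |
|---|---|---|---|
| Cohort A, after baseline, stops before Day 28 | baseline only, no post-baseline 24-h value | nothing | none |
| Cohort A, after Day 28, stops before Week 12 | baseline and Day 28 | nothing | Day-28 information lost |
| Cohort B, stops before the Week-12 biopsy | no change score | nothing | none |

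A patient already on the drug at baseline is a separate case: no unaffected data exist, and subject-level exclusion is defensible.

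**2. The plan's own figure**

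Protocol 12.8.1 gives 93% power for 15 enrolled in Cohort A with 20% loss: 15 × 0.80 = 12 evaluable. The effect and SD are redacted, so the 93% cannot be reproduced. Back-solving with a one-sample t test at one-sided 10% and n = 12 gives a standardised effect of 0.83; power is then 91% at n = 11 and 89% at n = 10. This is not the main issue, because a patient who must stop would not complete treatment under either rule.

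**3. Size of the shift**

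All effect values below are assumptions. Suppose k of N patients stop after Day 28 and baseline is similar in both groups. The mixed-model Week-12 mean is then approximately

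m + b × (k/N) × D,

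where m is the Week-12 mean log ratio of the others, b the slope of Week 12 on Day 28, and D how much worse the k patients are at Day 28 on the log scale. With deletion the estimate is m alone.

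*Set 1.* N = 15, k = 2, m = -0.60, SD 0.5 at both visits, correlation 0.6 (so b = 0.6), D = 0.8.

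- Deleted: exp(-0.60) = 0.549, a 45% reduction.
- Day 28 kept: 0.6 × (2/15) × 0.8 = 0.064; exp(-0.536) = 0.585 (0.586 by simulation), a 41% reduction.
- With k = 3, simulation gives 0.548 and 0.602, or 45% and 40%.

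This set is demanding. With a Day-28 mean of -0.35 in the others, the affected patients are at -0.35 + 0.8 = +0.45, and exp(0.45) = 1.57: a 57% rise in UPCR while still on treatment.

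*Set 2.* N = 12, k = 2; the others have ratios of 0.70 at Day 28 and 0.55 at Week 12; the affected patients have 1.0 at Day 28, so D = ln(1.0/0.70) = 0.357.

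- Deleted: 0.55, a 45% reduction.
- Day 28 kept, b = 0.7: 0.7 × (2/12) × 0.357 = 0.042; 0.55 × exp(0.042) = 0.573, a 43% reduction.
- b from 0.3 to 0.9: 0.560 to 0.580, or 44% to 42%.
- k = 1 or 3 with b = 0.7: 0.562 or 0.585.

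*No early difference.* If D = 0 the added term is zero, and both rules give 45%.

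**The case against.** The strongest reply is that Table 4-1 does what the protocol asks. Section 12.1 already restricts the PD set to subjects without PD-relevant deviations, and the table names one code that meets that test. On this reading 12.1 decides who is in the set and 12.4.3 decides how discontinuers within it are handled. That stands as far as it goes: a reader might infer that the SAP simply departs from the protocol, and the documents do not support that. The tension lies inside the protocol, and the SAP settles it by exclusion.

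The reply does not dispose of the point. The visible text of protocol 12.4 does not assign the primary analysis to the PD set; SAP section 6 does. Section 12.4.3 speaks directly about which data enter the primary analysis. A drug first taken after Day 28 cannot have affected a Day-28 value already collected. The SAP itself takes the narrower approach elsewhere: for Covid-19 interruptions, section 6.2.3 drops only the assessments after treatment discontinuation from the secondary analyses.

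A reader might also infer that patients who worsen are being removed from the primary analysis. The documents do not show this. The prohibited-medication list is redacted, only one code is visible, and the drug may have been taken for another reason. "Worsening of C3G disease" is a separate reason to stop in 9.1.1, and this code does not exclude a patient who stops for that alone. Protocol 6.2.3 lists rescue medication as not applicable. Finally, the sensitivity analyses are redacted, so one of them may already cover these patients.

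**Conclusion.** The conflict between protocol 12.4.3 and SAP Table 4-1 holds, and in Cohort A it can discard valid baseline and Day-28 data because of a post-baseline event. A bias in the primary estimate is possible but not demonstrated. Its direction depends on prohibited drugs being used more often by poor responders. Its size depends on those patients already being worse at Day 28: 45% with deletion against about 41% to 44% with earlier data kept, for two such patients under the assumptions shown. The change is nil if they look no different at Day 28 or stop before it. A Cohort B patient who stops before the Week-12 biopsy is unaffected by the choice of rule.

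It is tempting to compare deletion with a result that uses everyone's Week-12 value, which gives a 39% reduction in Set 1 and 39% to 34% in Set 2 (for Week-12 ratios of 1.0 to 1.6 in the affected patients). That overstates what is at issue, because 12.4.3 would not use values after discontinuation either.

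The study is described as non-confirmatory and the shift is modest, but it falls on the primary estimate and is cheap to avoid, so the change should be made.

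**What to change.** - In Table 4-1, for COMD02, replace removal of the subject with removal of assessments from the first use of the prohibited medication, or from treatment discontinuation if that is earlier. Keep earlier data in PD sets 1 and 2 for subjects who otherwise qualify. Subject-level exclusion may remain where the drug was already in use at baseline.
- Amend the PD-set definitions in SAP section 4 to match; changing the table alone would leave them contradicting it. State how the rule fits protocol 12.1 (impact judged by assessment) and 12.4.3 (which cuts at discontinuation, so cutting at first use is slightly stricter).
- Report the number of subjects affected, and run whole-subject exclusion as a sensitivity analysis.

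The cost is one table cell, matching wording in SAP section 4, one data-cut rule and one extra model run. Protocol 6.2.1 already has medication start dates recorded, so no new data are needed. The downside is a possibly slightly less favourable estimate.

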## 5 Statistical methods for Pharmacokinetic (PK) parameters

All subjects within the PK analysis set will be included in the PK data analysis.

#### 5.1 Variables

The following pharmacokinetic parameters of LNP023 will be determined using the actual recorded sampling times and non-compartmental analysis method(s) with Phoenix WinNonlin (Version 8 or higher):

- Plasma: Cmax, Tmax, AUClast, AUCtau and Ctrough (Cmin) after the first dose on Day 7, Day 14, Day 21 and Day 28 as well as Cmin on Days 92 and 99 (Week 13 and 14) Commercially Confidential Information
- Urine: Non-compartmental parameters, including but not limited to total cumulative urinary excretion (Ue) and renal plasma clearance (CLr).

Other pharmacokinetic parameters may be calculated as appropriate. All parameters determined are considered at steady state.

#### 5.2 Descriptive analyses

The following analyses will be implemented for each Cohort separately.

Individual LNP023 plasma and urine concentration data will be listed by treatment, subject, and visit/sampling time point, and plotted over time by subject. Descriptive summary statistics will be provided by treatment and visit/sampling time point,

Commercially Confidential Information . Pharmacokinetics parameters and will be listed by treatment and subject.

Summary statistics will include mean (arithmetic and geometric), SD, CV (arithmetic and geometric), median, minimum and maximum. An exception to this is Tmax where median, minimum and maximum will be presented. Commercially Confidential Information

A geometric mean will not be reported

if the dataset includes zero values.

All individual plasma concentration-time profiles for LNP023 concentration with median will be displayed graphically by treatment on semi-log view. In addition, the arithmetic mean (+/-SD) and geometric mean plasma concentration-time profiles for LNP023 by treatment over time will be displayed graphically on the linear and semi-log view.

Descriptive summary statistics of pharmacokinetic parameters will include mean (arithmetic and geometric), SD, and CV (arithmetic and geometric), median, minimum and maximum. An exception to this is Tmax where median, minimum and maximum will be presented.

## 6 Statistical methods for Pharmacodynamic (PD) parameters

All subjects within the PD analysis set 1 will be included in the PD data analyses of primary and secondary objectives.

All subjects within the PD analysis set 2 will be included in the PD data analyses of exploratory objectives.

#### 6.1 **Primary objective**

The primary objectives of this study are:

**Cohort A**: To evaluate the efficacy of LNP023 in reducing proteinuria at week 12, as assessed by ratio to baseline of Urine Protein to Creatinine concentration Ratio (UPCR) derived from 24-h urine collection in C3G subjects who have not received a kidney transplantation and have reduced C3 blood levels.

**Cohort B**: To assess histopathological changes in kidney biopsies at Week 12, as assessed by change from baseline in C3 Deposit Score (based on immunofluorescence microscopy) in C3G subjects who have received a kidney transplantation.

#### 6.1.1 Variables

The primary endpoints of this study are:

Cohort A: Ratio to baseline in UPCR derived from 24-h urine collection at Week 12.

Baseline is defined to be the 24-h urine collection on Day -1 to Day 1.

**Cohort B**: Change from baseline in C3 Deposit Score (based on immunofluorescence microscopy) at Week 12.

The C3 Deposit score varies from 0 to 3 graded intensity values for C3 deposition for the mesangial and capillary location. The score for each location (mesangial and capillary) will be multiplied with a factor of 1 for segmental and a factor of 2 for global extend. The total score range will therefore range from 0 to 12. Renal biopsy data includes C3 data.

The C3 Deposit score was chosen as the primary end-point in this the Phase 2 study due to close target relationship as the target of LNP023, Factor B, is required to cleave C3 during AP activation. Improvement is expected following a three-month treatment period. C3 deposition is C3G-defining; hence baseline C3G scores of subject included in this study will be elevated.

Baseline is defined to be the histopathological data obtained from a renal biopsy taken during run-in phase if the most recent renal biopsy is older than 3 months. If the renal biopsy is not older than 3 months, the baseline data will be provided by the site.

## 6.1.2 Descriptive analyses

**Cohort A**: UPCR from 24-h urine measurements will be listed by treatment, subject and visit/time and descriptive statistics of the raw and ratio to baseline will be provided by treatment and visit/time. Summary statistics will include mean (arithmetic and geometric), SD, CV (arithmetic and geometric), median, minimum and maximum as appropriate.

Graphical methods will be employed to show group and individual summary plots over time by treatment level.

**Cohort B**: The change from baseline in C3 Deposit score will be listed by treatment, subject and visit/time and descriptive statistics will be provided by treatment and visit/time. Summary statistics will include mean (arithmetic and geometric), SD, CV (arithmetic and geometric), median, minimum and maximum as appropriate.

Graphical methods and pictures will be employed to show group and individual summary plots over time by treatment.

**All Cohorts:** Overlaying individual time profiles (spaghetti plots) to visualize trends in raw UPCR 24h by time and treatment group will be created.

#### 6.1.3 Statistical model, assumptions and hypotheses

**Cohort A**: The log ratio to baseline in UPCR, will be analyzed using a mixed model repeated measures (MMRM), the analysis will include all data up to and including Week 12. This model will have the log ratio to baseline in UPCR as the dependent variable, baseline log transformed UPCR and time point (as study day relative to the start of study treatment, Day 28/29 and Day 84/85) as fixed effects. An unstructured covariance matrix will be used.

Model estimated means will be obtained at each timepoint, with Week 12 being of primary interest, along with the two-sided 80% confidence interval and p-value. Results will be back transformed to provide the geometric mean and their 80% CIs on the original scale.

Novartis	
SAP Addendum v02	

Model estimated means will be obtained at each timepoint, with Week 12 being of primary interest, along with the two-sided 80% confidence interval and p-value. Results will be back transformed to provide the geometric mean and their 80% CIs on the original scale.

**Cohort B**: The Wilcoxon signed rank test will be used for C3 Deposit Score data at Week 12 timepoint to compare the median difference of change from baseline between periods. The Hodges-Lehmann estimate and two-sided 80% confidence interval for the median difference will be provided.

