12.4.2 Statistical model, hypothesis, and method of analysis

12.4.2.1 Statistical Analysis:

Cohort A

The primary variable for assessing the effect of LNP023 is the log ratio to baseline UPCR derived from the 24h urine collections at Week 12.

A mixed model repeated measures (MMRM) will be fitted to the log ratio to baseline UPCR values over time. The model will include the log ratio to baseline UPCR as the dependent variable, time point (as study day relative to the start of study treatment) as a fixed effect, and baseline log transformed UPCR as a fixed covariate.

Baseline is defined to be the 24h urine collection on Day -1 to Day 1. An unstructured covariance matrix will be used

Results from this modelling will be presented as the estimated mean value of log UPCR at week 12 together with the 80% confidence interval. The results will be back transformed to provide the geometric mean and their 80% CIs on the original scale.

Cohort B

The primary variable for assessing the histopathological changes in kidney biopsies is week 12 change from baseline C3 Deposit Score.

The Wilcoxon signed rank test will be used for C3 Deposit Score data at Week12 time point to compare the median difference of change from baseline. The Hodges-Lehmann estimate and 80% confidence interval for the median difference will be provided.

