## 1.3.1. Exploratory objective(s)

#### 1.4 Study design and treatment

The study is a non-confirmatory, open-label, two cohort single arm, non-randomized study evaluating the efficacy, safety, tolerability, pharmacokinetics, pharmacodynamics and dose/biomarker relation of LNP023 in two subject populations:

- Cohort A: enrolls non-transplanted C3G subjects with reduced C3 serum levels Commercially Confidential Information
- Cohort B: enrolls subjects who have undergone kidney transplantation and have C3G recurrence.

Cohort B will start in parallel to Cohort A.

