#### 6.2.3 Statistical model, assumptions and hypotheses

The following statistical analyses will be implemented for each cohort separately and pooled cohorts. For subjects who stopped the study drug intake due to Covid-19 and restarted drug intake after tested negative to Covid-19 (i.e. OTHER-5 and with PD identifier OTH36), their assessments after treatment discontinuation will not be consider.

For each secondary variable (apart from hematuria, Bb and C3 biomarker) a similar statistical model will be used as described for the primary variable in Section 6.1.3.

Additionally, for Cohort B only, the log ratio to baseline in UPCR and UACR derived from 24h urine collection will also be analyzed with the same MMRM model as in Section 6.1.3.

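### In single-arm Cohort A, the baseline-adjusted MMRM gives a Week 12 80% CI and p-value that are too narrow for the population mean change whenever change is related to baseline.

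*SAP*

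**What the plan says.** SAP 1.4 describes the design: "The study is a non-confirmatory, open-label, two cohort single arm, non-randomized study". For Cohort A, SAP 6.1.3 models the log ratio to baseline: "This model will have the log ratio to baseline in UPCR as the dependent variable, baseline log transformed UPCR and time point", with two post-baseline time points ("Day 28/29 and Day 84/85) as fixed effects"). On the covariance it says: "An unstructured covariance matrix will be used". On reporting: "Model estimated means will be obtained at each timepoint, with Week 12 being of primary interest, along with the two-sided 80% confidence interval and p-value". Baseline is a single collection (SAP 6.1.1): "Baseline is defined to be the 24-h urine collection on Day -1 to Day 1".

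Protocol 12.4.2.1 gives the same model, "and baseline log transformed UPCR as a fixed covariate", and the same 80% interval. SAP 6.1 states the objective for C3G subjects without a kidney transplant and with reduced C3. Protocol 12.8.1 sizes the cohort for a one-sided 10% test.

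SAP 6.2.3 carries the model on: "a similar statistical model will be used as described for the primary variable". This covers the secondary variables other than hematuria, Bb and C3, in each cohort and pooled.

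Neither document states the baseline value at which the model mean is evaluated. No visible text adds a variance term for the estimated baseline mean.

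**The concern.** In a randomised trial the reported quantity is a difference between arms, and uncertainty in the overall baseline mean largely cancels from it. Here nothing cancels, because the adjusted mean is the result. Log UPCR at baseline is part of the dependent variable (log ratio = Week 12 minus baseline), so change is related to baseline unless Week 12 tracks baseline one for one. The covariate then removes baseline-related variation from the residual variance. The standard error does not put it back, although another sample of patients would have a different mean baseline and hence a different mean change.

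At stake are the coverage of the primary 80% interval and the error rate of the matching one-sided 10% test. Both err towards overstated precision. The renal secondary analyses inherit the same feature.

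**Working it through.** **The plan's own figure.** Protocol 12.8.1 gives 93% power with 15 subjects, one-sided 10%, 20% losses. The parts that can be checked agree: 15 × 0.80 = 12 completers, and a two-sided 80% CI matches a one-sided 10% test. The effect size and SD are blacked out, so 93% can be neither confirmed nor refuted. A one-sample t-test on 12 completers would need effect/SD of about 0.83 to reach it.

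**Formula.** Let b be baseline log UPCR and d the Week 12 log ratio. With complete data, the model mean at the observed mean of b is the plain mean of d.

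- Variance reported by the model: σ²_res / n.
- Variance over repeated samples of patients: (σ²_res + slope² × Var(b)) / n.
- Omitted term: slope² × Var(b) / n.

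This form takes the model's single baseline slope to hold at Week 12.

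**Inputs assumed, not in the documents.** rho is the correlation of baseline with Week 12 log UPCR, and v is the Week 12 SD divided by the baseline SD. Setting Var(b) = 1:

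- slope = rho·v − 1
- σ²_res = v²(1 − rho²)
- Var(d) = 1 + v² − 2·rho·v
- SE ratio (model / population) = √(σ²_res / Var(d)), which is √((1 + rho)/2) when v = 1

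For example, v = 1 and rho = 0.5 gives √0.75 = 0.87.

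**Results.** No true change, n = 12 complete, n − 2 df, single-visit form of the model, 100,000 simulated trials per row:

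| v | rho | SE ratio | 80% CI coverage | One-sided 10% test rejects |
|---|---|---|---|---|
| 1.0 | 0.3 | 0.81 | 70.5% | 14.8% |
| 1.0 | 0.5 | 0.87 | 73.6% | 13.2% |
| 1.0 | 0.7 | 0.92 | 76.7% | 11.7% |
| 1.0 | 0.8 | 0.95 | 77.8% | 11.2% |
| 1.0 | 0.9 | 0.97 | 79.1% | 10.5% |
| 0.8 | 0.3 | 0.71 | 64.5% | 17.8% |
| 0.8 | 0.7 | 0.79 | 69.9% | 15.0% |
| 1.2 | 0.3 | 0.87 | 74.3% | 12.7% |
| 1.2 | 0.7 | 0.98 | 79.5% | 10.3% |
| 1.2 | 0.9 | 0.99 | 79.7% | 10.1% |

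The paired t interval on the log ratio gave 80% coverage and 10% rejection in every row, to within 0.3 points.

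**Two-visit REML MMRM as specified.** With v = 1, n = 12 and 10,000 trials per value, coverage was 70.3%, 73.6%, 77.0%, 78.1% and 78.3% for rho 0.3, 0.5, 0.7, 0.8 and 0.9. Rejection was 15.2%, 13.1%, 11.2%, 11.1% and 10.8%. With a zero slope of change on baseline (v = 1.3, rho = 1/1.3) the model gave 80.8% and 9.5%, so there was no shortfall.

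**With losses.** With 15 patients and 3 missing Week 12 values (v = 1, rho 0.7 to 0.3, 1,500 trials per case), the planned model covered 78% to 72% and rejected 10.5% to 13.4%. With baseline as a response, coverage was 80% and rejection 9% to 11%. The simulation error on coverage here is about 1 point: √(0.8 × 0.2 / 1,500).

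**The case against.** Four arguments on the other side carry weight.

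- **The target.** Mean change at the observed mean baseline is a standard conditional quantity, and the interval is valid for it. This stands. However, neither document names that target, and the objective in SAP 6.1 speaks of a patient population.
- **The size is unknown.** The documents give neither rho nor v. Background therapy is held stable, so rho may be high. At rho 0.8 to 0.9 with equal variances the shortfall is only 1 to 2 points, and at v = 1.2 with rho of at least 0.7 it nearly vanishes. This stands, but it cuts both ways: a smaller SD at Week 12 makes it worse.
- **Status.** The study is non-confirmatory, and SAP 6.1.3.1 calls it exploratory. The one-sided 10% level appears only in the sample-size paragraph, and SAP 6.1.3 sets no success rule. This lowers the priority. It does not justify an interval whose stated 80% is not met for the population.
- **Other outputs.** SAP 6.1.2 provides the geometric mean and CV of the ratio to baseline, from which a reader could build an unadjusted interval. No such interval is planned as inference. The sensitivity analyses are blacked out, so I cannot say that no unadjusted analysis exists.

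A reader might infer that the estimated reduction is biased. With complete data it is not; only the stated precision is affected. A reader might also infer that the 93% power is wrong. Its inputs are blacked out, so that cannot be claimed.

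**Conclusion.** The point holds for the population mean change, provided the mean is evaluated at the observed mean baseline and change is related to baseline. Under equal variances, 12 complete patients and rho 0.3 to 0.9, the nominal 80% interval covers about 70% to 79%, and a one-sided 10% test rejects about 15% down to just over 10%.

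These figures illustrate the size and do not bound it. At v = 0.8 coverage fell to about 65% to 70%, and when change is unrelated to baseline there is no shortfall. Confidence is high in the mechanism and limited in the magnitude.

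A must-fix reading is tempting because the primary interval is affected. The documents do not support it: the study is non-confirmatory, no decision rule in SAP 6.1.3 depends on the p-value, and the complete-data estimate does not move. This is a recommended change, best made before the analysis.

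**What to change.** In SAP 6.1.3, and by reference 6.2.3, move log baseline UPCR from covariate to response. Use three time points (baseline, Day 28/29, Day 84/85), time as the only fixed effect, an unstructured covariance, and a named small-sample degrees-of-freedom method such as Kenward-Roger. Report the Week 12 minus baseline contrast, back-transformed, with its 80% CI and p-value. Keep the baseline-adjusted fit as supportive, and state the baseline value at which its mean is evaluated.

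An acceptable alternative is to keep the model and add slope² × s²_baseline / n to the variance of the Week 12 mean. In the n = 12 single-visit simulations above, this covered 81% to 82% and rejected about 9% to 9.5%, so it is slightly conservative.

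Simply dropping the covariate is not equivalent. Protocol 12.4.3 relies on missing at random, and if missing Week 12 values depend on baseline, the model needs baseline in it.

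The cost is a few sentences of SAP text and no new data. The unstructured matrix grows from three parameters to six, which is noticeable with 15 patients. The standard error rises by 1/(SE ratio): under equal variances about 3% at rho 0.9 (1/0.975) and 24% at rho 0.3 (1/0.806). It rises more if the Week 12 SD is below baseline, for example 26% at v = 0.8 and rho 0.7 (1/0.792).
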